8.1.4 Hospital Discharge Visit

The following procedures will occur if the subject is not discharged from the hospital on the same day as OHE resolution:

- Record all concomitant medications and AEs.
- Dispense Xifaxan 550 mg (BID dosing) and review instructions with subject.
- Schedule and review the open-label safety follow-up visits with subject.

8.1.5 Open-label Safety Follow-up / Visit 1 (Day 7 ±2)

Follow-up Visit 1 will occur 7 days (\pm 2 days) following a confirmed resolution of OHE. Note that OHE resolution and subject discharge may not occur on the same day.

- Record all concomitant medications and AEs.
- Collect vital sign measurements (include weight, supine blood pressure, heart rate, respiration rate and temperature).
- Complete a full physical examination, including evaluation for complications of liver cirrhosis.
- Collect blood and urine for clinical laboratory tests (hematology, blood chemistry, and urinalysis).
- Record date, time(s) and dose(s) of lactulose, if taken.
- Determine and record HEGI score. ([Appendix A](#))
- Determine and record WHC score. ([Appendix B](#))

Clinical Study Protocol, Amendment 3, dated 08 January 2020

CONFIDENTIAL

Page 43

- Assess health outcomes indices via CBI ([Appendix C](#)) and CLDQ ([Appendix D](#)).

8.1.6 Open-label Safety Follow-up Visit 2 (Day 14 ±2)

Follow-up Visit 2 will occur 14 days (\pm 2 days) following a confirmed resolution of OHE. Note that OHE resolution and subject discharge may not occur on the same day.

- Record all concomitant medications and AEs.
- Collect vital sign measurements (include weight, supine blood pressure, heart rate, respiration rate and temperature).
- Complete a full physical examination, including evaluation for complications of liver cirrhosis.
- Collect blood and urine for clinical laboratory tests (hematology, blood chemistry, and urinalysis).
- Record date, time(s) and dose(s) of lactulose, if taken.
- Determine and record HEGI score. ([Appendix A](#))
- Determine and record WHC score. ([Appendix B](#))
- Assess health outcomes indices via CBI ([Appendix C](#)) and CLDQ ([Appendix D](#)).

8.1.7 Open-label Safety Follow-up / Visit 3 (EOS) (Day 30 ±2)

Visit 3 (EOS) Visit will occur 30 days (\pm 2 days) following a confirmed resolution of OHE. Note that OHE resolution and subject discharge may not occur on the same day.

- Record all concomitant medications and AEs.
- Collect vital sign measurements (include weight, supine blood pressure, heart rate, respiration rate and temperature).
- Complete a full physical examination, including evaluation for complications of liver cirrhosis.
- Collect blood and urine for clinical laboratory tests (hematology, blood chemistry, and urinalysis).
- Record date, time(s) and dose(s) of lactulose, if taken.
- Determine and record HEGI score. ([Appendix A](#))
- Determine and record WHC score. ([Appendix B](#))
- Assess health outcomes indices via CBI ([Appendix C](#)) and CLDQ ([Appendix D](#)).
- Conduct urine pregnancy test.

If the subject discontinues or early terminates from the study during the open-label safety follow-up period, the Visit 3 (EOS) visit assessments will be followed as the subject early

termination/discontinuation visit and the subject exited from study. Please refer to [Section 8.3.1](#) for a list of early termination/discontinuation procedures to be conducted.

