5.0 STUDY DESIGN

5.1 Description of Study Design

Study RNHE2041 is a Phase 2, randomized, double-blind, placebo controlled, multicenter study evaluating the efficacy and safety of rifaximin SSD tablets (40 mg IR and 80 mg SER) plus lactulose in subjects hospitalized with OHE. Subjects who have liver cirrhosis and OHE, defined as a score of 2 or 3 on the Hepatic Encephalopathy Grading Instrument [[\(HEGI\); Appendix A](#)], are eligible for enrollment. Subjects who successfully meet the inclusion/exclusion criteria will enter the treatment period and will be randomized in a 1:1:1:1:1 ratio into 1 of 5 treatment groups as noted below. The blinded treatment period starts upon randomization following hospital admission.

Subjects will be on blinded treatment for up to 14 days. All subjects who complete the blinded randomized treatment phase (defined as confirmed resolution of OHE), will continue on to the safety follow-up period and receive 30 days of open-label treatment with Xifaxan® 550 mg upon hospital discharge, regardless of the treatment arm to which they were previously randomized. If subjects remain hospitalized following OHE resolution, standard of care treatment (which may include Xifaxan® 550 mg) should be given until hospital discharge. Open-label drug should only be dispensed to subjects upon hospital discharge. Please note this may be on a different day than OHE resolution.

- Treatment A: 40 mg immediate release (IR) rifaximin SSD tablet once daily (QD) and lactulose*.
- Treatment B: 40 mg immediate release (IR) rifaximin SSD tablet twice daily (BID) and lactulose*.

- Treatment C: 80 mg sustained extended release (SER) rifaximin SSD tablet once daily (QD) and lactulose*.
- Treatment D: 80 mg sustained extended release (SER) rifaximin SSD tablet twice daily (BID) and lactulose*.
- Treatment E: SSD placebo tablet twice daily (BID) and lactulose*.

*Oral Lactulose will be administered according to the product label, with dosage adjusted to produce 2 to 3 soft stools daily or per PI discretion. Rectal lactulose may be administered in lieu of oral lactulose. Bristol stool type will still be assessed as required by the protocol for subjects dosed with rectal lactulose. Dose amount and frequency for oral and rectal lactulose should be administered according to the product label or per PI discretion.

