5.5 Treatments

In the double-blind phase, subjects will be randomized (1:1:1:1:1) to the following treatment groups:

- Treatment A: 40 mg IR rifaximin SSD tablet once daily (QD)* and lactulose**.
- Treatment B: 40 mg IR rifaximin SSD tablet twice daily (BID) and lactulose**.
- Treatment C: 80 mg SER rifaximin SSD tablet once daily (QD)* and lactulose**.
- Treatment D: 80 mg SER rifaximin SSD tablet twice daily (BID) and lactulose**.
- Treatment E: SSD placebo tablet twice daily (BID) and lactulose**.

* Blinding will be maintained in the QD SSD cohorts by administering placebo as the second daily dose. All subjects will receive two tablet per day at 12-hour (± 2 hour) intervals based on the time of the first dose following randomization.

** The adult, oral dosage is 2 to 3 tablespoonfuls (30 to 45 mL, containing 20 to 30 gm of lactulose) TID. The dosage must be adjusted to produce 2 to 3 soft stools daily or per PI discretion. Rectal lactulose may be administered in lieu of oral lactulose. Bristol stool type will still be assessed as required by the protocol for subjects dosed with rectal lactulose. Dose amount and frequency for rectal lactulose should be administered according to product label or per PI discretion.

After completion of the blinded randomized treatment phase, defined as OHE resolution, subjects who continue on to the open-label safety follow-up period will receive 30 days of open-label treatment with Xifaxan® 550 mg upon hospital discharge, regardless of the treatment arm in which they were previously randomized. Open-label drug should only be dispensed upon hospital discharge. Please note this may be on a different day than OHE resolution. If subjects remain hospitalized following OHE resolution, standard of

Clinical Study Protocol, Amendment 3, dated 08 January 2020

CONFIDENTIAL

Page 28

care treatment (which may include Xifaxan® 550 mg) should be given until hospital discharge.

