8.0 STUDY METHODS

8.1 Study Visits

Following identification of a potential subject, the Investigator (or designee) will explain the purpose of the study, procedures, risks/benefits, and subject responsibilities to the potential subject's caregiver. The subject's ability to meet the requirements of the study will be determined in discussions with the caregiver. If the caregiver consents on behalf

Clinical Study Protocol, Amendment 3, dated 08 January 2020

CONFIDENTIAL

Page 38

of the subject the person obtaining written consent will sign and date the IRB/EC-approved ICF, at which point the subject is considered part of the study population. The original signed document will be retained in the subject records, and a copy will be provided to the subject/caregiver. In addition, the applicable privacy regulation requirements must be met.

Study Visit procedures are outlined in [Table 1](#).

Table 1: Study Design and Schedule of Assessments

	Blinded Randomized Treatment Period		Hospital Discharge	Open-label Safety Follow-up Period		
	Screening & Baseline	Treatment Period		Follow-up ⁴ Visit 1	Follow-up ⁴ Visit 2	Follow-up ⁴ Visit 3/ EOS ⁸
Study Day	Study Day 1	Study Day 2 Up to Study Day 15		Day 7 Post Resolution (±2)	Day 14 Post Resolution (±2)	Day 30 Post Resolution (±2)
Informed Consent	X					
Review inclusion / exclusion criteria	X					
Medical History and Demographics	X					
Record Concomitant Medications	X	X	X	X	X	X
Discontinue use of prohibited medications	X					
Vital Signs and Weight (kg)	X	X		X	X	X
Height (cm)	X					
Physical Examination	X	X ²		X	X	X
Clinical Laboratory Tests/ Urinalysis	X ⁵	X		X	X	X
Serum/Urine Pregnancy Test	X ⁶					X ⁶
HEGI ¹	X	X ²		X	X	X
WHC ¹	X	X ²		X	X	X
CBI ¹	X			X	X	X
Randomize Subject in EDC	X					
Dispense/Administer 1 st Dose of Blinded Study Drug		X ²				
Record dates/times of study drug dosing		X				
Record Bristol Stool Appearance		X				
Record lactulose use (dosing time and amount) dates/times of lactulose use	X	X		X ³	X ³	X ³
Assess Open-Label Dosing Compliance				X ³	X ³	X ³
Record Adverse Events	X	X	X	X	X	X
Dispense Open Label Xifaxan® 550mg and Review Dosing Instructions			X ⁷			
CLDQ ¹				X	X	X

Abbreviations: EOS = end of study

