All Subject assessments will be performed by a trained and qualified Evaluator. Efforts should be made to have the same evaluator assess the same Subject for as many HEGI assessments as possible. Every effort must be made for the same Evaluator to conduct the HEGI assessments at both the resolution of OHE and the confirmation of resolution assessed 3 to 12 hours later.

¹Evaluator, defined by only licensed physicians, physician's assistants or nurse practitioners, who are trained in these instruments may conduct the assessment.

²Assessments are conducted twice per day, approximately 12 hours (±2 hours) apart. Following resolution of OHE, a confirmatory HEGI (3 to 12 hours post initial resolution) must be done to complete the blinded randomized treatment phase.. Subjects should continue to dose on blinded study medication until OHE resolution is confirmed.

³Subject will report on lactulose use (if any) and open-label dosing compliance from previous visit to current visit. Diary cards are not being used on this study.

⁴Open-label Safety Follow-up visits will be conducted by a study investigator.

⁵Clinical laboratory tests run within 24 hours of consent, may be used in place of drawing new labs at Screening provided all protocol required labs are present. Note: AFP is only required at Screening.

⁶ Serum pregnancy test is done at Screening and urine pregnancy test at EOS visit (open-label safety follow-up Visit 3)

⁷ Open-label drug should only be dispensed to subjects upon hospital discharge. Please note this may be on a different day than OHE resolution.

⁸ If a subject early terminates/discontinues during the study, the visit schedule at the end of the that treatment phase should be followed for their ET visit.

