8.4 Concomitant Medications/Therapy

All concomitant medications administered within 30 days of Day 1 (Screening/Baseline) will be recorded in the subject's medical records and case report form (CRF).

Permitted Therapy

1. Direct-acting antivirals and hepatitis B virus suppression therapy permitted following AASLD guidelines.

2. Stable dose of antidepressants and/or benzodiazepines if the dose and regimen are expected to remain unchanged throughout the trial.
3. Prescription and non-prescription sleep aids [e.g., Lunesta™ (eszopiclone) and Intermezzo® or Ambien® (zolpidem tartrate)].
4. Stable dose of Neurontin (gabapentin) and Lyrica (pregabalin) if the dose and regimen are expected to remain unchanged throughout the trial.
5. Diuretics (including diuretics for the management of ascites).

Prohibited Therapy

Any prohibited medications used during the study will be recorded on the concomitant medication page of the CRF.

1. Non-study rifaximin (e.g., commercial rifaximin, Xifaxan® 550 mg tablets), Rifampin or other rifamycin derivatives are prohibited upon subject consent to the study.

Note: After completion of the blinded randomized treatment phase, defined as OHE resolution, subjects will who continue on to the open-label safety follow-up period will receive 30 days of open-label treatment with Xifaxan® 550 mg upon hospital discharge, regardless of the treatment arm in which they were previously randomized. Open-label drug should only be dispensed upon hospital discharge. Please note this may be on a different day than OHE resolution.

If subjects remain hospitalized following OHE resolution, standard of care treatment (which may include Xifaxan® 550 mg) should be given until hospital discharge,, at which time the subjects will receive 30 days of open-label Xifaxan® 550 mg.

The following concomitant medications are prohibited within 30 days of Day 1 (Screening/Baseline) and throughout the study:

1. Milk thistle.
2. Investigational drug product or device used within 30 days or 5 drug half-lives (whichever is longer) prior to Baseline.
3. P-glycoprotein inhibitors: including but not limited to cyclosporine A, non-selective beta blockers (excluding nadolol), HIV protease inhibitors, azole antifungals, macrolide antibiotics, non-dihydropyridine calcium channel blockers. NOTE: This is NOT A COMPLETE LIST.

The following concomitant medications are prohibited after Day 1 (Screening/Baseline) through the EOS visit:

1. P-glycoprotein inhibitors.

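### The end-of-study visit is timed from OHE resolution but the 30-day open-label course starts at discharge, so a late discharge can leave dosing days after the last scheduled safety contact

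*Combined protocol and SAP*

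**What the plan says.** Two clocks run in the open-label phase.

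- **Visits.** Sections 8.1.5 to 8.1.7 and Table 1 time all three follow-up visits from confirmed resolution. For the last one, the "Visit 3 (EOS) Visit will occur 30 days" after resolution, with a window of ±2 days.
- **Treatment.** Section 5.1 says: "Open-label drug should only be dispensed to subjects upon hospital discharge". Section 5.5 repeats this, and note 7 to Table 1 adds: "Please note this may be on a different day than OHE resolution". Under section 8.4, a subject who stays in hospital after resolution receives standard of care until discharge, "at which time the subjects will receive 30 days of open-label" Xifaxan. The in-hospital days are therefore not deducted from the 30.

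Section 8.1.3 lists dispensing among the resolution procedures. Section 8.1.4 then provides a separate discharge visit "if the subject is not discharged from the hospital on the same day as OHE resolution", so dispensing belongs to discharge. No maximum lag is set between resolution and discharge, and Table 1 schedules no contact after EOS.

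Two other provisions depend on EOS. The only scheduled pregnancy test after baseline is the urine test at EOS (Table 1, note 6). One list in section 8.4 opens: "The following concomitant medications are prohibited after Day 1 (Screening/Baseline) through the EOS visit". It names P-glycoprotein inhibitors, warfarin and certain supplements.

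**The concern.** The synopsis describes the follow-up phase as the period in which subjects take 30 days of open-label treatment, and its stated purpose is safety. A subject discharged some days after resolution can nevertheless reach the last scheduled visit with tablets still to take. For those final days no visit will collect laboratory values, ask about adverse events or check compliance. Note 3 to Table 1 makes compliance a matter of recall from one visit to the next, without diary cards, so dosing after EOS is never recorded. The pregnancy test will have been done before exposure ends, and the section 8.4 list tied to EOS will have lapsed during dosing.

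The readmission endpoint in section 7.1 is also touched. A subject can be readmitted only after discharge, so a 30-day period counted from resolution gives a late-discharged subject fewer than 30 days at risk.

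**Working it through.** The plan states no figure to reproduce here, so the check is date arithmetic.

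**Inputs.** Day 0 is confirmed resolution. EOS is nominally day 30 and may be held from day 28 to day 32 (Table 1, 8.1.7). The open-label course lasts 30 days and starts at discharge (5.1, 5.5, 8.4). Discharge is on day g, which the documents do not give; the values below are assumptions.

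**Formulas.** The protocol does not say whether the first open-label dose is taken on the day of discharge, so both cases are shown.

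- First dose on the day of discharge: last dosing day is g + 29. Dosing days after an EOS on day v are max(0, g + 29 − v), which is max(0, g − 1) for v = 30.
- First dose on the next day: last dosing day is g + 30. Dosing days after EOS are max(0, g + 30 − v), which is g for v = 30.

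**Dosing days left after EOS (first dose on discharge day / next day):**

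| g | EOS day 28 | EOS day 30 | EOS day 32 |
|---|---|---|---|
| 0 | 1 / 2 | 0 / 0 | 0 / 0 |
| 1 | 2 / 3 | 0 / 1 | 0 / 0 |
| 2 | 3 / 4 | 1 / 2 | 0 / 0 |
| 3 | 4 / 5 | 2 / 3 | 0 / 1 |
| 4 | 5 / 6 | 3 / 4 | 1 / 2 |
| 5 | 6 / 7 | 4 / 5 | 2 / 3 |
| 7 | 8 / 9 | 6 / 7 | 4 / 5 |
| 14 | 15 / 16 | 13 / 14 | 11 / 12 |

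With EOS on day 30 and the first dose on the day of discharge, the uncovered share of the course is 2/30 = 7% at g = 3, 4/30 = 13% at g = 5 and 6/30 = 20% at g = 7.

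**Threshold.** With EOS on day 32, the latest day allowed, all dosing is covered when g + 29 ≤ 32, that is g ≤ 3, or when g + 30 ≤ 32, that is g ≤ 2. For longer lags some dosing follows EOS wherever the visit sits in its window.

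**Readmission.** Time at risk between discharge and day 30 is 30 − g days: 25 at g = 5 and 23 at g = 7.

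**The case against.** The resolution anchor looks deliberate. Sections 8.1.5 to 8.1.7 each acknowledge that resolution and discharge may fall on different days. The anchor places HEGI, WHC, CBI and CLDQ at a common time from the event that ends the blinded phase. That is a real benefit, but it does not deal with the exposure left uncovered.

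The size is unknown. For short lags the window may absorb the problem, and nothing in the documents shows how often discharge comes 4 or more days after resolution. This stands.

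There are also backstops. SAEs up to 30 days after stopping study drug are reportable if the investigator learns of them (9.4), and related SAEs remain reportable later (9.3.2). Pregnancies must be reported within 24 hours with no stated cut-off at EOS (9.9). Unscheduled visits are allowed (8.1.8), and known adverse events are followed (8.2, 9.7). Xifaxan is already approved to reduce recurrence of OHE (3.4.2). These keep the harm modest, but they depend on awareness or discretion and do not replace scheduled laboratory tests, routine inquiry or the pregnancy test.

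A reader might go further and infer that adverse event collection stops at EOS, or that the contraception commitment does. The documents do not say so. Section 9.3.1 includes the 30-day open-label period, so collection can be read as running to the end of the course; what is missing is a scheduled contact at which to collect. Section 5.2.1.1 ties contraception to participation, and a subject still taking trial-supplied drug may count as participating. Likewise, P-glycoprotein inhibitors also appear in a second list in section 8.4 that applies for the whole study, so their ban lapses at EOS only if the study is taken to end there. The warfarin ban is tied to EOS alone.

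**Conclusion.** The mismatch is real and its effect is modest. With EOS on day 30, g − 1 dosing days (g with next-day dosing) follow the last scheduled contact. Once the lag exceeds 3 days (2 with next-day dosing), no placement of EOS within its window covers the whole course. With same-day discharge and EOS on day 30 or later, nothing is uncovered.

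This rests on the full 30-day course being taken and on a lag that the documents do not give, so how many subjects are affected cannot be stated. It also reads study drug in section 9.4 as including the open-label tablets.

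The loss is end-of-course safety and compliance data on a marketed drug in an uncontrolled phase. It would be wrong to infer any effect on the primary endpoint, power or comparisons between arms: the primary endpoint is reached before the open-label course begins. The change is worth making because it is cheap.

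**What to change.** In Table 1 and section 8.1.7, set Visit 3/EOS at 30 days after discharge (first open-label dose), with a window of 0 to +2 days. EOS then falls between day g + 30 and day g + 32, and the last dosing day is g + 29 or g + 30, so no dosing day follows EOS for any g. At most the final day's doses remain, if EOS is held on the last dosing day. A ±2 window around the new date would not achieve this: EOS on day g + 28 would still leave 1 or 2 dosing days. Keep Visits 1 and 2 timed from resolution, and in section 7.1 count readmission over 30 days from discharge.

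**Cost.** Protocol wording and one changed anchor, with no extra visit. The final HEGI, WHC, CBI and CLDQ would vary in time from resolution by g, and the last HEGI and WHC fixed to resolution would be those at Visit 2 (day 14). The CBI and CLDQ endpoints run to study exit, so their definitions still fit. With a long lag, Visits 1 and 2 can still precede open-label dosing.

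**Fallback.** If an assessment fixed at day 30 after resolution is wanted, keep EOS as it is, add a phone contact at the end of the course for adverse events and compliance, and run the prohibited-medication and contraception rules to the last open-label dose. That adds one contact and does not recover the laboratory tests or the pregnancy test.

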8.1.8 Unscheduled Visits

Additional visits may be scheduled, as necessary, to ensure the safety and well-being of subjects. All additional exams should be fully documented in the source documents and on Unscheduled Visit CRFs, as appropriate. Visits intended to fulfill scheduled visit requirements that fall outside the designated scheduled visit range, are not Unscheduled Visits. In these cases, the visit data will be collected and transcribed to the appropriate scheduled visit CRF.

If a subject is seen for multiple visits during a given visit timeframe, the data from the visit that is intended to meet the protocol requirements for the scheduled visit, should be captured on the visit CRF. Where such a determination cannot be made, the first visit within the scheduled visit interval will be used for completion of the protocol required scheduled visit CRF. Data from any additional visits within a scheduled visit interval will be captured on an Unscheduled Visit CRF.

8.1.9 Missed Visits

If a subject misses any scheduled follow-up visit and cannot be seen prior to the start of the visit range for the next scheduled follow-up visit, the visit is considered missed.

8.2 Post-Study Follow-up

If a subject requires further follow-up of AEs upon discontinuation or completion of the study, the Investigator should schedule post-study follow-up visits, as necessary. Refer to [for follow-up of AEs following study exit.](#)

